## 2 Study objectives

**Primary objective:** Primary objective of the study is to evaluate the safety and efficacy of canakinumab on the clinical and inflammatory findings of BD patients with neurologic and vascular involvement.

**Secondary objectives:** Secondary objectives include analyses measuring the effects of canakinumab on radiological findings (neurologic and vascular), cerebrospinal fluid findings (neurologic), and [REDACTED] aiming to investigate the biology of inflammatory attacks and their response to IL-1 blockade in parallel with clinical findings.

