### **5.5.6 Rescue medication**

A rescue treatment with increased doses of prednisolone or intravenous methyl prednisolone pulses could be used depending on worsening of BD manifestations at the discretion of the investigator.

If no response or worsening of neurologic/vascular manifestations were observed in the first week, rescue treatment decision should be given with the repeated CSF and MRI (neurologic) or CT/Doppler (vascular) analyses.

Following protocol will be used as rescue treatment in patients with worsening symptoms:

For patients with neurologic involvement: 5-10 days of 1000 mg intravenous methyl prednisolone, followed by 1 mg/kg/day prednisolone, if still an insufficient response is observed, 1000 mg intravenous cyclophosphamide

For patients with vascular involvement: 3 days of 1000 mg intravenous methyl prednisolone, followed by 1 mg/kg/day prednisolone, if still an insufficient response is observed, 1000 mg iv cyclophosphamide.

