## 5.7 Patient demographics/other baseline characteristics

Patient demographic and baseline characteristic data to be collected on all patients include: date of birth, age, sex, ethnicity, patient referral source, relevant medical history/current medical condition present before signing informed consent. Where possible, diagnoses will be recorded, not symptoms.

Subjects should be seen for all post-baseline visits on the designated day with the allowance of a  $\pm 7$  day window for all visits. Subjects who discontinue study drug before completing the study, and those who prematurely withdraw from the study for any reason, should be scheduled for a visit 8 weeks ( $\pm 1$  week) after their last infusion /injection, at which time all of the assessments listed for the final visit will be performed.

Subjects who discontinue study drug also should return for a last assessment. If they refuse to return for this or are unable to do so, every effort should be made to contact them or a knowledgeable informant by telephone to determine the reason for discontinuation. At a minimum, they will be contacted for safety evaluations during the 30 days following the last dose of study drug, including final contact at the 30-day point. Documentation of attempts to contact the patient should be recorded in the patient record.

Information that will be collected on subjects who are screened but not enrolled includes patient demographics (age, gender, and ethnicity) and primary reason for not continuing.

If a patient discontinues before entering Visit 1, only the demographic information and Screening Log entry with the primary reason for discontinuation should be completed on the CRF. It is not necessary to complete all the required evaluations at the time of discontinuation unless medically indicated.

At screening visit information on age, sex, will be collected. Relevant medical history/current medical conditions, family medical history, will be recorded on the respective CRF page. The following should be recorded on the respective CRF page.

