### **8.5.2 Safety variables**

The assessment of safety will be based mainly on the frequency of adverse events, which includes all serious adverse events. Adverse events will be summarized by the number and percentage of subjects having any adverse event, having an adverse event in each body system and having each individual adverse event. Any other information collected (e.g. severity or relatedness to study medication) will be listed as appropriate.

Newly occurring notable laboratory values and newly occurring vital sign abnormalities will be tabulated. Listings with abnormalities flagged will be provided

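### Adverse-event percentages in 8.5.2 are not split at rescue, so they cannot be read as rates on canakinumab without rescue

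*Combined protocol and SAP*

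**What the plan says.** Section 2 puts safety in the primary objective: "Primary objective of the study is to evaluate the safety and efficacy of canakinumab on the clinical and inflammatory findings of BD patients". Section 8.4.1 lists no safety item among the primary variables; adverse events are handled under secondary variables.

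Section 8.5.2 sets the method: "The assessment of safety will be based mainly on the frequency of adverse events, which includes all serious adverse events". The tables are subject counts: "Adverse events will be summarized by the number and percentage of subjects having any adverse event, having an adverse event in each body system", and so on down to the individual event. For the rest: "Any other information collected (e.g. severity or relatedness to study medication) will be listed as appropriate". Section 8.1 defines the safety population as patients with at least one dose and one post-baseline assessment. Rescue does not remove a patient from it.

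Section 5.5.6 describes rescue for worsening disease: 1000 mg methylprednisolone for 5–10 days (neurologic) or 3 days (vascular), then prednisolone 1 mg/kg/day, and for neurologic patients "if still an insufficient response is observed, 1000 mg intravenous cyclophosphamide". The vascular sequence ends with the same cyclophosphamide dose. A rescue decision is foreseen after lack of response or worsening in the first week.

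Follow-up after stopping is set in several places. Under 5.7, patients who stop drug or withdraw "should be scheduled for a visit 8 weeks" (±1 week) after their last dose, with all final-visit assessments; those who do not return are contacted at least over the 30 days after the last dose. Section 6.2.2 requires reporting of every serious adverse event until 30 days after the last dose, and after that only if a link to study treatment is suspected. Section 5.5.10 says that data up to discontinuation from the study are analysed.

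**The concern.** Pulsed steroid and cyclophosphamide can themselves cause infections and laboratory changes. The trial has one arm, no comparator and about 10 patients, all enrolled during an acute exacerbation, so rescue is foreseeable. Nothing in section 8 cuts off, flags or separately tabulates events by rescue. The only attribution item is the investigator's yes/no judgement of relatedness to study medication in an open-label study, and it is listed rather than tabulated. A reader of the planned table could not tell whether, for example, a serious-infection percentage arose before or after rescue. That reader would be using the main evidence on half of the primary objective.

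**Working it through.** The plan states no safety rate, rescue rate or power figure, so there is no planned number to reproduce. The check covers step size, the time in which post-rescue events can accrue, and time at risk.

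**Step size.** N = 10 (sections 5 and 8.7). One patient adds 1/10 = 10 percentage points. Exact (Clopper-Pearson) 95% intervals:

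| Patients with event | Percentage | 95% interval |
|---|---|---|
| 0/10 | 0% | 0 to 30.8% |
| 1/10 | 10% | 0.3 to 44.5% |
| 2/10 | 20% | 2.5 to 55.6% |

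Assumed example: two patients have an infection only after rescue and nobody has one before. The planned table shows 20%; a table restricted to pre-rescue onset shows 0%.

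**Expected size under assumed rates.** Let q0 be the risk of an event without rescue, q1 an independent added risk from rescue, and k the number rescued out of 10. The expected all-events percentage is

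[(10 − k)·q0 + k·(1 − (1 − q0)(1 − q1))]/10 = q0 + (k/10)(1 − q0)·q1.

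| q0 | k | q1 = 20% | q1 = 40% |
|---|---|---|---|
| 10% | 1 | 11.8% | 13.6% |
| 10% | 3 | 15.4% | 20.8% |
| 10% | 5 | 19.0% | 28.0% |
| 30% | 1 | 31.4% | 32.8% |
| 30% | 5 | 37.0% | 44.0% |

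These rates are illustrations; the documents give none.

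**Time in which post-rescue events can accrue.**
- Dropped at Day 30 after a single Day 0 dose, under the 30-day limits (6.2.2, and the safety contact in 5.7): 30 − 30 = about 0 days.
- Same patient, under the 8-week visit in 5.7: 56 ± 7 = Days 49–63; minus 30 gives 19–33 days.
- Rescued on Day 7 with no further dose: 30 − 7 = 23 days under the 30-day limits, or 49 − 7 = 42 to 63 − 7 = 56 days under the 8-week visit.
- Rescued on Day 7 and kept on study: up to 360 − 7 = 353 days.

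Which case applies is unsettled. Section 5.5.8 prohibits cyclophosphamide and corticosteroids at or above 20 mg/day during the study, and 5.5.9 requires study drug to stop when prohibited medication is used, yet 5.5.6 provides for both as rescue. These sections must be reconciled. Rescue in the first week leaves some post-rescue time under any of the rules above.

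**Time at risk before rescue.** A patient rescued on Day 7 contributes 7 pre-rescue days, against up to 360 for one never rescued. With two patients rescued on Day 7 and eight followed to Day 360 (assumed), pre-rescue time is 8 × 360 + 2 × 7 = 2,894 patient-days, about 80% of 10 × 360 = 3,600. A pre-rescue percentage over all 10 patients hides this difference.

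**The case against.** The strongest reply is that 8.5.2 plans a descriptive frequency of all adverse events in the safety population, and as such it is correct. That stands. A reader might infer that the reported percentage is a wrong canakinumab rate, but the plan never presents it as a causal rate for canakinumab.

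A reader might also infer that every event up to an 8-week exit visit is counted after rescue. The documents do not say so. Section 8.5.2 gives no event window, and the pooling follows from the absence of a rule. The 30-day limits in 5.7 and 6.2.2 restrict capture, most clearly for serious events later blamed on rescue. Section 5.5.10 leaves open whether events after a patient is dropped are analysed at all.

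Third, a table restricted to pre-rescue onset does not isolate canakinumab harm. Rescue selects worsening patients, cuts their time short, and a later infection may reflect canakinumab and steroid together. This also stands, and it limits what the fix can claim. Nor would that table describe canakinumab alone: 5.9.4 allows baseline prednisolone up to 20 mg, and isoniazid may be given alongside.

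Finally, event dates, relatedness and medications are already recorded, and 10 patients can be read one by one. That makes the split cheap. It does not make it planned: without a rule, the choice of which events to set apart would be made after the data are seen.

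**Conclusion.** The point holds as a limit on interpretation. The planned percentages are valid as all-event frequencies but cannot be read as rates on canakinumab without rescue. Calling them the primary safety result would go too far: safety is in the primary objective, but 8.4.1 names no safety variable and no safety threshold exists.

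The size is 10 percentage points for each patient whose only event of a type follows rescue, at N = 10. The actual distortion is unknown and would be nil if nobody were rescued. For a patient dropped at Day 30 after one dose, post-rescue events can accrue for about 0 days up to 19–33 days, and for longer if rescue starts earlier or the patient stays on study. The conclusion rests on reading the silence of section 8 as no split, and on rescued patients staying in the safety population as 8.1 defines it. The change is worth making because it is small and concerns half of the primary objective.

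**What to change.** In 8.5.2:

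- Keep the all-events summary.
- Add a summary of events with onset before the first dose of rescue or of any other new immunosuppressant. Report with it the number of patients rescued and the time at risk before rescue, for example as events per patient-time.
- Flag post-rescue onset in the listings.
- State that post-rescue events may still involve canakinumab, so the pre-rescue table supplements the all-events table and does not replace it.

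Reconcile 5.5.6 with 5.5.8 and 5.5.9 on steroids and cyclophosphamide, since the amount of post-rescue follow-up depends on it.

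The cost is one extra table and a link between medication start dates and event onset dates. Section 6.1 already collects event start dates. Sections 5.5.7 and 5.8 require medications to be recorded, but 5.8 names only medication name and reason, so capture of start dates must be confirmed. No added visits or patients are needed.

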### **5.5.7 Concomitant treatment**

The investigator should instruct the patient to notify the study site about any new medications he/she takes after the patient was enrolled into the study. All medications, procedures and significant non-drug therapies (including physical therapy and blood transfusions) administered after the patient was enrolled into the study must be recorded.

### **5.5.8 Prohibited Treatment**

The following treatments are NOT allowed prior to baseline (time intervals prior to baseline are detailed below) AND during the entire study:

- Etanercept in the 4 weeks prior to the baseline visit (Day 0) and thereafter
- Riloncept in the 3 weeks prior to the baseline visit (Day 0) and thereafter
- Adalimumab in the 8 weeks prior to the baseline visit (Day 0) and thereafter
- Infliximab in the 12 weeks prior to the baseline visit (Day 0) and thereafter
- Rituximab in the 26 weeks prior to the baseline visit (Day 0) and thereafter
- Any other investigational biologics in the 8 weeks prior to the baseline visit (Day 0) and thereafter (with the exception of anakinra therapy –see below)
- Kineret (anakinra therapy) 3 days prior to the baseline visit (Day 0) and thereafter
- Leflunomide in the 4 weeks prior to the baseline visit (Day 0) and thereafter. After the completion of leflunomide treatment a cholestiramine in dose 8 g 3 times per day for 14 days is recommended.
- Thalidomide in the 2 weeks prior to the baseline visit (Day 0) and thereafter
- Cyclosporine in the 2 weeks prior to the baseline visit (Day 0) and thereafter
- i.v. immunoglobulin (i.v. Ig) in the 8 weeks prior to the baseline visit (Day 0) and thereafter
- 6-Mercaptopurine, cyclophosphamide, or chlorambucil in the 12 weeks prior to the baseline visit (Day 0) and thereafter
- Dapsone, in the 3 weeks prior to the baseline visit (Day 0) and thereafter
- Corticosteroids  $\geq 20\text{mg/day}$  or  $>0.4 \text{ mg/kg}$ , whichever applies, in the 1 week prior to the baseline visit (Day 0) and thereafter
- Live vaccinations within 3 months prior to the start of the trial, during the trial, and up to 3 months following the last dose.
- Use of other investigational non-biological drugs at the time of enrollment, within 30 days or 5 half-lives of enrolment, whichever is longer.
  - Intravenous methyl prednisolone pulse treatment within the last month

The investigator should instruct the patient to notify the study site about any new medications he/she takes after the start of the study drug. All medications and significant non-drug therapies (including physical therapy and blood transfusions) administered after the patient starts treatment with study drug must be listed on the Concomitant medications/Significant non-drug therapies after start of study drug.

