## 2.1 Primary objective(s)

**Primary endpoint:** Resolution of acute exacerbation findings related to BD based on achievements in any of the following items without deterioration on day 30:

**For patients with parenchymal neurologic disease:** Resolution of acute exacerbation of parenchymal neurologic findings based on improvements in any of the following items without deterioration on Day 30:

- a. Improvement of muscle strength, ataxia, or other relevant neurologic findings depending on the involved region on neurological examination (by NBDS, Modified EDSS, and modified Rankin scores)
- b. Improvement in systemic inflammatory findings (CRP, ESR, SAA)
- c. Any decrease in the size of the MRI lesion, or disappearance of contrast enhancement
- d. Improvement in patients' and physicians global assessment using a 10-cm visual analogue scale (VAS)

**Complete response** will be defined as full clinical recovery to the pre-attack state, disappearance of MRI lesion(s), and normalisation of CSF findings.

**Partial response** will be defined as partial improvement in clinical findings, but with findings still worse than the pre-attack state, and MRI lesions, which become smaller with no or less enhancement, and a decrease in CSF cell count.

**Non-response** will be defined as no improvement in clinical findings, no change on MRI, no change in CSF parameters, or worsening in those findings.

**For patients with large vessel vascular disease:** Resolution of acute vascular exacerbation findings related to BD based on achievements in any of the following items without deterioration at 1 month:

- a. Improvement in relevant symptoms (localised pain, abdominal pain, calf thickness, haemoptysis) by using physician and patient's global assessment with VAS
- b. Improvement in systemic inflammatory findings (CRP, ESR, SAA)
- c. Any improvement in radiological findings depending on the involved vessels (MR, CT or Doppler findings)
- d. Improvement in patients' and physicians global assessment using a 10-cm visual analogue scale (VAS)

**Complete response** will be defined as clinical and laboratory improvement based on  $\geq 50\%$  improvements in patient's and physician's global assessments by using VAS, and  $\geq 50\%$  reduction in CRP values; along with stable or  $\geq 20\%$  reduced aneurym size in patients with arterial involvement, and stable or  $\geq 20\%$  reduced calf swelling in patients with lower extremity venous thrombosis.

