#### **Key exclusion criteria**

##### **For NBS:**

1-Presence of severe neurological sequelae from any previous attacks rendering the patient dependent on others physically or mentally

2-Any other neurological cause underlying the picture including ischemic CNS lesion on MRI

3-Any previous treatment with biological agents other than interferon-alpha or any previous treatment with cyclophosphamide

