#### ***General***

7- Presence or history of any other inflammatory rheumatic disease

8- Use of the listed treatment

- c. interferon-alpha in the last 6 months,
- d. IVMP in the past month

9- Positive PPD test (according to local guidance) where an active TB infection cannot be excluded via Quantiferon (T-Spot or radiographic imaging if needed) If PPD test or Quantiferon-Gold assay result shows latent TB infection without signs of active tuberculosis disease, patient will be allowed to enter in the study, when the patient agrees to start taking isoniazid prophylaxis along with the study drug for 9 months.

10- Pregnancy or lactation

11-Presence of any active or chronic infection or any major episode of infection requiring hospitalization or treatment with i.v. antibiotics within 30 days or oral antibiotics within 14 days prior to screening

12-History of a malignancy within the last 5 years, except for successfully excised squamous or basal cell carcinoma of the skin

13-Women of childbearing potential not using the contraception method(s) specified in this study, as well as women who are breastfeeding

14-With known sensitivity to canakinumab

15- Use of any other investigational agent in the last 30 days

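### A Day 30 response reached after Section 5.5.6 rescue can count as a canakinumab response, because no visible rule says how a rescued patient is scored

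*Combined protocol and SAP*

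**What the plan says.** Section 5.5.6 on who may be rescued: "A rescue treatment with increased doses of prednisolone or intravenous methyl prednisolone pulses could be used depending on worsening of BD manifestations", at the investigator's discretion. On timing: "If no response or worsening of neurologic/vascular manifestations were observed in the first week, rescue treatment decision should be given", supported by repeat CSF and MRI, or CT/Doppler. The neurologic regimen is "5-10 days of 1000 mg intravenous methyl prednisolone, followed by 1 mg/kg/day prednisolone". The vascular regimen has 3 pulse days in place of 5-10. Both go on to 1000 mg intravenous cyclophosphamide if the response is still insufficient.

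Section 2.1 defines the primary endpoint as "Resolution of acute exacerbation findings related to BD based on achievements in any of the following items without deterioration on day 30". Complete, partial and non-response, there and in 5.9.1, rest on clinical state, VAS, CRP, imaging and, for neurologic disease, CSF.

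Section 8.1 puts everyone with at least one dose in the intent-to-treat set. The per-protocol set needs study completion without major deviations, which are not defined. Section 8.4.1 lists the percentage of complete responders. Section 8.4.2 states the efficacy claim as at least 50% response in at least half the patients, with all parameters compared with baseline.

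Section 5.5.8 is headed "The following treatments are NOT allowed prior to baseline (time intervals prior to baseline are detailed below) AND during the entire study". Its list includes cyclophosphamide and corticosteroids of 20 mg/day or more. Section 5.5.9 makes use of prohibited medication a reason to stop study drug. Section 5.9.4 says prednisolone should not be increased during the trial.

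**The concern.** The trial has one arm and no comparator, so the efficacy claim rests on each patient's change by Day 30. Rescue is strong treatment aimed at the same findings that define response, and it can be given and take effect before those findings are scored. If a patient fails to improve in week 1, receives methylprednisolone pulses and is better at Day 30, the plan gives no instruction on whether that is a response to canakinumab. Two sites could score the same course differently, and the final count would not show which responses followed rescue. The same gap applies to a patient who starts or increases another immunomodulator after Day 0.

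**Working it through.** **Timing.** Rescue may be decided in the first week; take a start at the Day 7 visit. The longest pulse course then runs from Day 7 to Day 16, and the 3-day course from Day 7 to Day 9. Section 5.7 allows 7 days either side of each visit, so the Day 30 assessment falls between Day 23 and Day 37. Even the longest course ends at least a week before scoring.

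**Does any visible rule assign a response status?**
- *Response definitions (2.1, 5.9.1).* They compare the Day 30 state with baseline or, for neurologic recovery, the pre-attack state. None mentions rescue. The endpoint asks for no deterioration on Day 30, so week 1 worsening that rescue has reversed does not clearly fail it.
- *Dropping non-responders at month 1 (3.1, 5.5.5).* This follows the physician's scoring, which is the undefined step.
- *Stopping study drug (5.5.9).* No response status is attached. The second dose is not due until Day 30, so stopping earlier changes no dosing before the assessment.
- *Analysis sets (8.1).* Intent-to-treat keeps the patient. The per-protocol set may drop the patient, but dropping is not the same as counting a non-response.
- *Primary analysis (8.4.1, 8.4.2).* No condition on co-therapy.

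**Size.** The documents give no power, effect size or rescue rate, so there is no stated figure to reproduce. Inputs:
- n = 10 (Sections 5 and 8.7).
- Pass mark of 5 responders in 10: an assumed reading of 8.4.2.
- p, the response rate on canakinumab alone: assumed.
- r, the chance that a patient who would not respond to canakinumab alone is rescued before Day 30: assumed 10%, 25% or 50%.
- e, the chance that a rescued patient is scored a responder: assumed 5-10% or 30-60%.

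Apparent response rate: p' = p + (1 − p) × r × e.
Pass chance: the sum over k = 5 to 10 of C(10,k) p'^k (1 − p')^(10−k).

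Without rescue the pass chance is 3.3%, 15.0% and 36.7% at p = 20%, 30% and 40%.

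Example at p = 30%, r = 25%, e = 60%: p' = 0.30 + 0.70 × 0.25 × 0.60 = 0.405, and the pass chance is 38%. The full set at p = 30%, against 15% without rescue:

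| r | Expected rescued (10 × 0.7 × r) | e = 5% | e = 10% | e = 30% | e = 60% |
|---|---|---|---|---|---|
| 10% | 0.7 | 16% | 16% | 19% | 23% |
| 25% | 1.75 | 17% | 18% | 25% | 38% |
| 50% | 3.5 | 18% | 22% | 38% | 65% |

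Over the same r, at p = 20% the pass chance goes from 3% to 4-7% (e = 5-10%) or 5-47% (e = 30-60%). At p = 40% it goes from 37% to 37-44% or 41-80%.

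**After the fix.** In this model only patients who would not otherwise respond are rescued, so the extra count has rate p and its pass chance at 30% returns to 15%. If instead 1 or 2 patients receive added therapy regardless of response and are set to non-response, 5 responders are needed from the other 9 or 8, and the pass chance at 30% falls to 10% or 6%. The count is therefore conservative.

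**The case against.** **The worsening limb.** Non-response includes worsening, and 5.5.6 gives its regimens for patients whose symptoms worsen. On a reasonable reading, a patient rescued for worsening is already a non-responder. This stands as a reading but not as a rule: scoring is at month 1, when the worsening may have reversed, and the first-week decision also covers patients who simply have not responded.

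**A Day 30 score may not exist.** If rescue triggers 5.5.9, Section 5.7 schedules a visit 8 weeks after the last infusion, about Day 56 for a patient dosed only on Day 0. This is fair, but the glossary separates stopping treatment from leaving the study, and it is unclear whether rescue allowed by 5.5.6 counts as prohibited use. A reader might infer that rescued patients will certainly be credited to canakinumab. The documents show only that they can be.

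**Complete response is hard to reach.** Neurologic complete response needs full recovery, disappearance of MRI lesions and normal CSF, so 30-60% may be far too high for that group. This stands; hence the 5-10% range. The vascular criteria (VAS, CRP, stable size) look easier to meet after steroids.

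**One-patient margins.** A reader might infer that most passes would turn on one rescued patient, since 68% of passes at a true 30% without rescue have exactly 5 responders. That model contains no rescued patients. With rescue and e = 30-60%, the share runs from 66% down to 38%, and those passes need not include a rescued responder.

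**Interferon-alpha.** A reader might infer that 5.5.8 permits it on study, because it is not named and exclusion 8 covers only "interferon-alpha in the last 6 months". The documents do not support that. The catch-all bars "Any other investigational biologics in the 8 weeks prior to the baseline visit (Day 0) and thereafter", and exclusion 3, in the words "Any previous treatment with biological agents other than interferon-alpha", treats interferon-alpha as a biological agent. The text is ambiguous, and nothing suggests interferon-alpha would be started before Day 30.

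**Exploratory pilot.** The study is not powered and its target is an aim. That limits the weight of the probabilities, but 8.4.2 still sets a condition for claiming efficacy.

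**Conclusion.** The point holds for rescue. On the visible text, a Day 30 response reached after 5.5.6 rescue can count towards the canakinumab efficacy claim, and no section requires otherwise. The certain part of the size is that one patient in 10 is 10 percentage points. The pass probabilities depend on assumed rescue rates, an assumed scoring rate and the 5-of-10 reading. At a true 30% the effect runs from almost nothing (15% to 16%) to large (15% to 65%), and the documents do not say where in that range the trial would fall. Attribution is weak in any single-arm study of acute attacks: spontaneous recovery and permitted low-dose steroids remain whatever is done. Rescue differs because it is recorded and can be separated. Part of 8.1 is redacted; if a scoring rule stands there, the point falls.

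**What to change.** In 8.4.2, keep the count as written and report a second beside it. In the second count, intent-to-treat patients who received 5.5.6 rescue, or who started or increased another immunomodulator, between Day 0 and the Day 30 assessment are non-responders and stay in the denominator. Start the window at Day 0, not at attack onset. An earlier start would turn patients with recently begun background treatment into automatic non-responders without a reason.

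Record start date and dose of these drugs and list the patients concerned. State that the two counts show sensitivity to co-therapy and do not bracket the drug's true effect.

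The cost is one extra count, one listing and a few CRF fields. Steroid use is already assessed at every visit, and concomitant drugs are already recorded and coded, but 5.8 specifies only medication name and reason. The downside is that the second count is conservative, because some rescued patients might have responded anyway. Access to rescue does not change.

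Naming interferon-alpha in 5.5.8 would be a useful clarification but is optional. So would a statement of whether 5.5.6 rescue triggers 5.5.9.

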### **5.5.9 Discontinuation of study treatment**

Study drug must be discontinued for a given patient if the investigator determines that continuing it would result in a significant safety risk for that patient. The following circumstances require study drug discontinuation:

- Emergence of the following adverse events:
  - in the case of any severe or serious adverse event that is not compatible with administration of study medication, including adverse events that require treatment with an unacceptable co-medication,
  - in the case of onset of malignancy,
  - in the case of an uncontrolled life-threatening infection.
- Pregnancy
- Use of the prohibited concomitant medications
- Withdrawal of informed consent

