### **5.9.4 Steroid Tapering**

Prednisolone dosage should be 20 mg or less at baseline, and it should not be increased during the trial.

At the end of Day 30, complete responders begin to decrease the steroid doses. Tapering target will be 2,5 mg for every 2 weeks. At Day 120, patients expected to use prednisolone no more than 5 mg / day.

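### The steroid limits in 5.5.8 and 5.9.4 contradict each other at 20 mg/day, and 5.5.9 read literally would then require stopping canakinumab

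*Combined protocol and SAP*

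**What the plan says.** Section 5.5.8 (Prohibited Treatment) lists treatments not allowed before baseline or during the study. For corticosteroids it gives two limits, at or above 20 mg/day and above 0.4 mg/kg, joined by *or* and followed by "whichever applies, in the 1 week prior to the baseline visit (Day 0) and thereafter".

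Section 5.9.4 (Steroid Tapering) sets the background dose: "Prednisolone dosage should be 20 mg or less at baseline, and it should not be increased during the trial". It then describes the taper. The start is given as "At the end of Day 30, complete responders begin to decrease the steroid doses". The planned reduction is 2.5 mg per fortnight, and the end point of the taper is given as "At Day 120, patients expected to use prednisolone no more than 5 mg / day".

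Section 5.5.9 (Discontinuation of study treatment) introduces its list with "The following circumstances require study drug discontinuation", and one entry is "Use of the prohibited concomitant medications".

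Section 5.5.6 (Rescue medication) allows more steroid in one situation: "A rescue treatment with increased doses of prednisolone or intravenous methyl prednisolone pulses could be used depending on worsening of BD manifestations".

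**The concern.** One section includes 20 mg/day in what it prohibits, and the other includes it in what it permits. A site with a patient on 20 mg cannot tell from the protocol whether that patient may be treated. If the patient is treated under 5.9.4 and someone later applies 5.5.8, 5.5.9 makes stopping canakinumab mandatory.

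Three things depend on which section a site follows: whether the patient enters, whether dosing continues, and whether the patient can contribute to the steroid-tapering variable in 8.4.1. Per-protocol membership under 8.1 may also be affected. Deviation handling cannot settle the question, because the sections disagree on whether 20 mg is a deviation at all. Section 10 adds that requests to approve deviations will not be granted. The study plans about 10 patients, so one patient is 1/10, or 10 percentage points, of any responder percentage.

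**Working it through.** **Inputs.** From 5.5.8: prohibited if dose ≥ 20 mg/day or dose > 0.4 mg/kg. From 5.9.4: permitted at baseline if dose ≤ 20 mg, with no later increase; for complete responders, a 2.5 mg reduction every 2 weeks from the end of Day 30, and no more than 5 mg/day at Day 120. Body weights below are assumed; the documents give none.

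**The plan's own figure.** From 20 mg to 5 mg takes (20 − 5) / 2.5 = 6 steps. If the first step is on Day 30, the sixth is on Day 30 + 5 × 14 = Day 100. If the first step is on Day 44, the sixth is on Day 30 + 6 × 14 = Day 114. Both precede Day 120, so the target can be met from 20 mg. This shows only that 20 mg is compatible with the schedule.

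**Absolute limit.** At 20 mg/day, 20 ≥ 20 is true, so 5.5.8 prohibits the dose. Also 20 ≤ 20 is true, so 5.9.4 permits it. The overlap of ≥ 20 and ≤ 20 is the single value 20 mg.

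**Weight limit.** 0.4 mg/kg equals 20 mg at 20 / 0.4 = 50 kg. If the lower limit binds, the doses that 5.9.4 permits and 5.5.8 prohibits are:

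| Assumed weight | 0.4 mg/kg | Doses in conflict |
|---|---|---|
| 40 kg | 16 mg | above 16, up to 20 mg |
| 45 kg | 18 mg | above 18, up to 20 mg |
| 50 kg or more | 20 mg or more | exactly 20 mg |

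**The other reading.** *Whichever applies* could mean that only one limit governs a given patient. If that were the weight limit alone, 20 mg would be prohibited only below 50 kg. The protocol does not say which limit governs whom.

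**Would changing one symbol be enough?** If 5.5.8 barred > 20 mg/day instead of ≥ 20 mg/day, 20 mg would pass the absolute limit. A patient of 49.9 kg on 20 mg would still exceed the weight limit, since 0.4 × 49.9 = 19.96 mg. The rule for combining the limits also has to be fixed.

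**Does another section reconcile them?** Rescue in 5.5.6 covers increased doses for worsening disease, not a stable background dose. Section 5.5.10 says deviations should not lead to withdrawal unless they indicate a significant safety risk; that concerns leaving the study and does not cancel the drug-stopping rule in 5.5.9. Section 4.2 excludes recent intravenous methylprednisolone, and 4.1 refers to earlier high-dose steroid in neurologic patients without giving a dose. None of these decides the status of 20 mg/day.

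**The case against.** The strongest reply is that the conflict is narrow and rarely bites. Section 5.9.4 sets a ceiling; it tells no one to use 20 mg. Any dose below 20 mg/day and not above 0.4 mg/kg satisfies both sections. At 50 kg or more the clash is one dose value, and the wider band at lower weights depends on how an unclear phrase is read. This stands and fixes the size of the point. Still, 20 mg is the value that both sections use as their boundary.

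A second reply is that forced stopping needs a mixed reading. A site following 5.5.8 would not dose the patient, and a site following 5.9.4 would not see 20 mg as prohibited. Stopping arises only when entry follows 5.9.4 and 5.5.8 is enforced afterwards. That is correct, so the consequence is conditional. It remains possible, for example when a monitor checks protocol adherence under 7.1.

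A third reply is that the data are largely protected. Section 8.1 presents results for everyone who took at least one dose, 5.5.10 says data up to discontinuation will be analysed, and per-protocol exclusion for a deviation needs it to be major. Nothing says a breach at the boundary would be major. This stands too, so loss from the per-protocol set is a possibility and not an established result.

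**Conclusion.** The contradiction is real and the documents do not resolve it. It covers exactly 20 mg/day and, if the lower limit binds, doses above 0.4 mg/kg and up to 20 mg in patients under 50 kg. The clash at 50 kg or more assumes that the absolute limit applies to those patients, which is the ordinary reading of two limits joined by *or*. The number of patients on such doses is unknown, and no size or direction of bias is claimed. It should be corrected because it leaves entry and continued dosing undefined.

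Three stronger readings are tempting and not supported:

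- A reader might infer from the taper that 20 mg was the intended starting dose. Lower starts also meet Day 120: 17.5 mg needs (17.5 − 5) / 2.5 = 5 steps and reaches 5 mg on Day 86 or Day 100. The schedule cannot tell less than 20 mg from 20 mg or less.
- A reader might infer that patients must stay on 20 mg until Day 30. Section 5.9.4 forbids an increase and says when complete responders start to reduce; it does not require the dose to be held until then.
- A reader might infer that the weight limit, taken alone, lets heavier patients start above 20 mg. Section 5.9.4 caps baseline prednisolone at 20 mg independently.

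**What to change.** Use one identical limit in 5.5.8 and 5.9.4, in prednisolone equivalents, because 5.5.8 speaks of corticosteroids and 5.9.4 of prednisolone. There are two ways to align the absolute limit:

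- Bar only doses above 20 mg/day in 5.5.8. Cost: patients on exactly 20 mg are clearly admitted, so some have a slightly higher background steroid dose at baseline.
- Write less than 20 mg in 5.9.4. Cost: patients on exactly 20 mg are clearly excluded, which may matter for recruitment in a study of about 10.

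The choice is clinical; either removes the contradiction in the absolute limit.

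Then replace *whichever applies* with a stated rule, for example whichever is lower, and repeat that two-part limit in 5.9.4. Alternatively, delete the weight-based limit. Keeping it as the lower limit restricts patients under 50 kg further; deleting it gives up that restriction. Either way the change is protocol wording only, with no new assessments or data.
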